Grade 1	
Continue protocol therapy.
 
Monitor creatinine weekly.
	
If returns to baseline:
 
Resume routine creatinine monitoring per protocol
 
If worsens:
 
Treat as Grade 2-3 or 4

Table 5: Renal Adverse Event Management

Note: Rule out non-inflammatory causes. If non-inflammatory cause, treat accordingly and continue protocol therapy.

Grade of Creatinine Elevation	Management	Follow-Up
Grade 2 – 3	
Delay protocol therapy
 
Monitor creatinine every 2-3 days
 
Administer 0.5 to 1.0 mg/kg/day methylprednisolone IV or oral equivalent
 
Consider renal biopsy with nephrology consult as clinically appropriate
	
If returns to Grade 1:
 
Taper steroids over at least 1 month, consider prophylactic antibiotics for opportunistic infections, and resume protocol therapy and routine creatinine monitoring per protocol
 
If elevations persist > 7 days or worsens:
 
Treat as Grade 4

Grade 4	
Permanently discontinue protocol therapy
 
Monitor creatinine daily
 
Administer 1.0-2.0 mg/kg/day methylprednisolone IV or IV equivalent
 
Consult nephrologist and consider renal biopsy as clinically appropriate
	
If returns to Grade 1:
 
Taper steroids over at least 1 month and add prophylactic antibiotics for opportunistic infections

Patients on IV steroids may be switched to an equivalent dose of oral corticosteroids (e.g. prednisone) at start of tapering or earlier, once sustained clinical improvement is observed. Lower bioavailability of oral corticosteroids should be taken into account when switching to the equivalent dose of oral corticosteroids.
		

Table 6: Pulmonary Adverse Event Management

Note: Rule out non-inflammatory causes. If non-inflammatory cause, treat accordingly and continue protocol therapy. Evaluate with imaging and pulmonary consultation as clinically appropriate.

Grade of Pneumonitis	Management	Follow-Up
Grade 1	
Consider delay of protocol therapy
 
Monitor for symptoms every 2-3 days
 
Consider Pulmonary and ID consults
	
Re-image at least every 3 weeks
 
If worsens:
 
Treat as Grade 2 or \geq Grade 3.

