Symptomatic Endocrinopathy	
Evaluate endocrine function
 
Consider pituitary scan
 
Symptomatic with abnormal lab/pituitary scan:
 
Delay protocol therapy
 
Administer 1-2 mg/kg/day methylprednisolone IV or PO equivalent
 
Initiate appropriate hormone therapy
 
No abnormal lab/pituitary MRI scan but symptoms persist:
 
Repeat labs in 1-3 weeks / MRI in 1 month
	
If improves (with or without hormone replacement):
 
Taper steroids over at least 1 month and consider prophylactic antibiotics for opportunistic infections
 
Resume protocol therapy
 
Patients with adrenal insufficiency may need to continue steroids with mineralocorticoid component

Table 8: Endocrinopathy Adverse Event Management

Note: Rule out non-inflammatory causes. If non-inflammatory cause, treat accordingly and continue protocol therapy. Consider visual field testing, endocrinology consultation, and imaging.

Event	Management	Follow-Up
Suspicion of adrenal crisis (e.g. severe dehydration, hypotension, shock out of proportion to current illness)	
Permanently discontinue protocol therapy
 
Rule out sepsis
 
Stress dose of IV steroids with mineralocorticoid activity
 
Administer IV fluids
 
Consult endocrinologist as clinically appropriate
 
If adrenal crisis ruled out, then treat as above for symptomatic endocrinopathy
	

Patients on IV steroids may be switched to an equivalent dose of oral corticosteroids (e.g. prednisone) at start of tapering or earlier, once sustained clinical improvement is observed. Lower bioavailability of oral corticosteroids should be taken into account when switching to the equivalent dose of oral corticosteroids.

Table 9: Skin Adverse Event Management

Note: Rule out non-inflammatory causes. If non-inflammatory cause, treat accordingly and continue protocol therapy.

Grade of Rash^A	Management	Follow-Up
Grade 1 – 2	Continue protocol therapy. Administer symptomatic therapy (e.g. antihistamines, topical steroids)	If persists > 1-2 weeks or recurs: Consider skin biopsy Delay protocol therapy Consider 0.5-1.0 mg/kg/day methylprednisolone IV or oral equivalent. Once improving, taper steroids over at least 1 month, consider prophylactic antibiotics for opportunistic infections, and resume protocol therapy If worsens: Treat as Grade 3-4

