Grade of Amylase or Lipase Elevation, Pancreatitis	Management^B	Follow-Up
Asymptomatic Grade 1 ^A	Continue protocol therapy. Monitor amylase and lipase weekly until resolution to baseline.	Resume routine protocol monitoring. If worsens: Treat as Grade 2-3 or 4.
Asymptomatic Grade 2-3 ^A	Delay protocol therapy. Monitor amylase and lipase weekly until resolution to baseline.	If improves to baseline: Resume protocol therapy and routine protocol monitoring. If worsens: Treat as Grade 4.
Asymptomatic Grade 4 ^A	Permanently discontinue protocol therapy. Monitor amylase and lipase weekly until resolution.	Monitor patient until resolution to baseline.
Any Symptomatic Elevations in Amylase/Lipase, Pancreatitis	Permanently discontinue protocol therapy. Consider GI consult as clinically appropriate. Administer supportive care.	Monitor patient until resolution to baseline.

- A. Patients should be monitored for signs/symptoms consistent with pancreatitis, including abdominal pain and vomiting.
- B. Corticosteroids do not seem to alter the natural course of amylase/lipase elevations.

Table 12: Ocular Adverse Event Management		
Note: Rule out non-inflammatory causes. If non-inflammatory cause, treat accordingly and continue protocol therapy. Work-up for ocular adverse events should also consider pituitary inflammation as a potential cause.		
Event Grade	Management^A	Follow-Up
Grade 1	
Continue protocol therapy.
 
Monitor patient for worsening symptoms.
 
Consider ophthalmologist consult as clinically appropriate.
 
Administer topical corticosteroids as clinically indicated.
	
If worsens:
 
Treat as Grade 2 or \geq Grade 3.

Grade 2	
Delay protocol therapy.
 
Obtain ophthalmologist consult.
 
Administer topical corticosteroids as clinically indicated.
	
If improves to baseline:
 
Resume protocol therapy.
 
If worsens:
 
Treat as \geq Grade 3.

\geq Grade 3	
Permanently discontinue protocol therapy.
 
Obtain ophthalmologist consult.
 
Administer systemic corticosteroids as clinically indicated.
	
Monitor patient until resolution to baseline.
 
Taper systemic corticosteroids as clinically appropriate.

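### Table 8 stops therapy permanently on suspicion of adrenal crisis, then sends patients in whom crisis is ruled out to a row that delays and resumes therapy

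*Combined protocol and SAP*

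**What the plan says.** Section 6.1, Table 8 (endocrinopathy management) has a row whose trigger is a suspicion: "Suspicion of adrenal crisis (e.g. severe dehydration, hypotension, shock out of proportion to current illness"). The management cell opens with "Permanently discontinue protocol therapy", with no condition attached. It then asks for sepsis to be ruled out, stress-dose steroids, fluids and an endocrinology consult as appropriate. It closes with "If adrenal crisis ruled out, then treat as above for symptomatic endocrinopathy".

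The row it points to, symptomatic endocrinopathy, delays therapy when labs or the pituitary scan are abnormal. If the patient improves, with or without hormone replacement, its follow-up column says "Resume protocol therapy". Its other branch, for normal findings with persisting symptoms, only repeats tests and stops nothing.

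The header note over the whole table adds: "If non-inflammatory cause, treat accordingly and continue protocol therapy. Consider visual field testing, endocrinology consultation, and imaging".

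**The concern.** The first and last lines of one cell give opposite dosing instructions for the same patient: one in whom adrenal crisis was suspected and then excluded. The first line has already ended therapy for good, while the last leads to delay and resumption.

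What is at stake is how that participant is managed. Followed literally, the first line permanently removes from first-line treatment a patient who did not have the event. Section 5.5 then has the reason and date of removal entered in the case report form, and it describes no route back. The triggers (dehydration, hypotension, shock) are non-specific, so exclusions are foreseeable, and the row itself provides for them.

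**Working it through.** No plan figure needs reproducing. The check sets the instructions side by side and then looks at how the protocol uses the same wording elsewhere.

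**1. The patient in whom crisis is ruled out**

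| Source | Drug action |
|---|---|
| Table 8, suspected crisis, first line | Permanent stop |
| Table 8, suspected crisis, last line, leading to the symptomatic row with abnormal labs or scan | Delay; resume on improvement |
| Same, with normal labs and MRI | Repeat tests; no stop stated |
| Table 8 header note, if the cause is non-inflammatory (e.g. sepsis) | Continue |

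The first entry is incompatible with each of the other three. No footnote to Table 8 lifts the permanent stop, and neither do Section 5.5 (off-therapy criteria), 6.2 (delays) or 6.3 (no dose reductions).

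**2. What *treat as* means in these tables**

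Instructions counted in Tables 4 to 13:

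| Table | *Treat as* another row | Permanent discontinuation |
|---|---|---|
| 4 | 2 | 1 |
| 5 | 2 | 1 |
| 6 | 2 | 1 |
| 7 | 1 | 1 |
| 8 | 1 | 1 |
| 9 | 1 | 1 (footnote A) |
| 10 | 2 | 1 |
| 11 | 2 | 2 |
| 12 | 2 | 1 |
| 13 | 0 | 1 |
| Total | 15 | 11 |

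- Outside Table 8 there are 15 − 1 = 14 *treat as* instructions. Each moves the patient to a higher-grade row that states a drug action.
- In 13 of those 14 the possible target rows include permanent discontinuation. The exception is Table 9, whose Grade 3–4 row allows either delay or discontinuation.
- Table 5 is one example: Grade 2–3 creatinine elevation that persists or worsens becomes "Treat as Grade 4", a row that stops therapy permanently. Table 11 is another: "If worsens: Treat as Grade 4" leads to "Permanently discontinue protocol therapy. Monitor amylase and lipase weekly until resolution". In both, the switch carries the drug decision as well as the medical care.
- Table 8's instruction is the only one of the 15 that moves a patient out of a permanent-discontinuation row.
- It also contains the only one of the 11 permanent stops that is triggered by a suspicion.

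Read as the other 14 are read, Table 8's last line brings in the delay and resume rules, and these cannot coexist with a permanent stop.

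**3. How the protocol writes such distinctions elsewhere**

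- Table 9 footnote A withholds therapy when Stevens-Johnson syndrome or toxic epidermal necrolysis is suspected, and discontinues permanently only on diagnosis.
- Table 7 footnote A states explicitly when delay may replace discontinuation.
- Section 2.2.6 treats a suspected inflammatory event as the stage at which other causes are to be excluded.

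Table 8 has no equivalent wording.

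**4. Size**

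Section 2.4.4 lists adrenal insufficiency and hypophysitis among drug-related serious events seen in more than 2 subjects per cohort, in cohorts of 31 to 40 on related regimens. The row may therefore be used. Those events are not suspected crises later excluded, and no rate for the latter is given, so no patient count can be derived.

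**The case against.** The strongest defence is that the last line is conditional. A default followed by an exception in the same cell is ordinary drafting, and the exception governs. An investigator who reads to the end would probably hold and then resume. That is likely how the row would be applied, and it limits the harm. But it concedes that the stop on suspicion is really a hold, which makes *permanently* the wrong word, and nothing in the text says that the last line overrides the first.

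A second defence is that the last line concerns medical care only (steroids, hormones, repeat tests) while the stop stands. The tables do sometimes separate treatment from drug action, as in the header notes. The 14 comparators also all escalate, so they show that a row switch can add a stop, not that it can cancel one. That is a fair limit on the counting argument: intent is inferred, not stated. Still, this reading departs from every other row switch in Tables 4 to 12, and it leaves the conflict with the header note, under which a patient whose shock proves septic continues therapy.

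Third, caution is defensible when shock is among the triggers, and Section 2.2.6 generally favours permanent discontinuation of ipilimumab for severe inflammatory events. That guidance concerns severe events as such, not suspicions later excluded. Toxic epidermal necrolysis, which appears among the toxic deaths in Section 2.4.4 under the earlier regimens, is handled by withholding first.

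Finally, Section 5.5 requires immediate notice to the Overall PI for unusual or life-threatening complications, so a case with shock should be discussed promptly. This reduces the risk of a literal stop but does not tell either party which line applies.

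**Conclusion.** The concern holds. As written, the cell gives incompatible dosing instructions for a patient in whom suspected adrenal crisis is ruled out, and no other text reconciles them. That much rests on the wording alone. The further conclusion, that the intent is to hold on suspicion and stop permanently only on confirmation, is an inference from the protocol's usage in its other tables.

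Severity is minor. The reach is limited to suspected and then excluded crises, and harm requires literal use of the first line. Patients who stop before progression are still followed for response (Sections 5.6 and 11.1), so the response analysis rules and the Simon boundaries and error rates do not change.

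**What to change.** Reword the first and last lines of the cell on the model of Table 9 footnote A, for example: *Withhold protocol therapy while adrenal crisis is suspected; permanently discontinue if confirmed. If ruled out, manage as symptomatic endocrinopathy, including its delay and resume rules; if the cause is non-inflammatory (e.g. sepsis), follow the header note.*

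Drug still stops at once on suspicion, and for good on confirmation. The hold needs no new limit, because Section 6.2 already allows delays of up to 6 weeks for nivolumab and 12 weeks for ipilimumab, with exceptions approved by the principal investigator.

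The cost is two lines in one table cell of a protocol amendment, with no added visits, tests or patients.

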6.2 Dose Delays

Dosing of ipilimumab or nivolumab may be held at the treating investigator's discretion for any toxicity of any grade. Additionally, holding of the study agents may be required as indicated in the tables in **Section 6.1**.

A treatment delay of up to six weeks for nivolumab and up to 12 weeks for ipilimumab is allowable. Participants requiring a longer hold should be removed from protocol therapy. Exceptions for participants exhibiting clinical benefit may be possible with approval from the principal investigator.

If study agent dosing is held due to toxicity, the counting of cycle days and assessment schedule will continue without interruption. For example, a participant who does not receive their Cycle 3

Day 15 dose of nivolumab due to toxicity will proceed with their next regularly scheduled clinic visit (Cycle 3 Day 29) as previously planned. Additional interim clinic visits may be scheduled to manage toxicity, however the cycle will not restart due to dosing delays due to adverse events and the assessment schedule (including tumor imaging evaluations) will continue as originally planned.

6.3 Dose Reductions

There will be no dose reductions for nivolumab or ipilimumab allowed. Participants who cannot tolerate the assigned doses of nivolumab or ipilimumab should be removed from protocol therapy.

6.4 Overdose Management

There is no available information concerning overdose with nivolumab or ipilimumab. In case of overdose, patients must be closely monitored for signs or symptoms of adverse reactions and appropriate symptomatic treatment instituted. There are no specific antidotes.

7. ADVERSE EVENTS: LIST AND REPORTING REQUIREMENTS

Adverse event (AE) monitoring and reporting is a routine part of every clinical trial. The following list of reported and/or potential AEs (**Section 7.1**) and the characteristics of an observed AE (**Section 7.2** and **Section 7.3**) will determine whether the event requires expedited reporting **in addition** to routine reporting.

7.1 Expected Toxicities

7.1.1 Adverse Events List

In addition to the list below, please also refer to the investigator's brochure (IB) for both nivolumab and ipilimumab for comprehensive adverse event information.

7.1.1.1 Adverse Event List for Nivolumab combined with Ipilimumab

Common adverse events associated with combination treatment include:

- Fatigue
- Fever
- Chills
- Flu-like symptoms
- Infusion-related reactions
- Headache
- Dizziness
- Hyperthyroidism or hypothyroidism
- Cough
- Dyspnea

- Pneumonitis
- Hypotension
- Dry mouth
- Anorexia
- Diarrhea
- Nausea
- Vomiting
- Dehydration
- Abdominal pain
- Colitis
- Elevated liver transaminases
- Elevated lipase and/or amylase
- Rash
- Pruritus
- Vitiligo
- Joint pain or stiffness
- Muscle soreness, weakness, stiffness, or spasms

7.2 Adverse Event Characteristics

An adverse event (AE) is defined as any new untoward medical occurrence or worsening of a pre-existing medical condition in a clinical investigation participant administered study drug. It does not necessarily have a causal relationship with this treatment. An AE can therefore be any unfavorable and unintended sign (such as an abnormal laboratory finding), symptom, or disease temporally associated with the use of investigational product, whether or not considered related to the investigational product.

- **CTCAE term (AE description) and grade:** The descriptions and grading scales found in the revised NCI Common Terminology Criteria for Adverse Events (CTCAE) version 4.0 will be utilized for AE reporting. All appropriate treatment areas should have access to a copy of the CTCAE version 4.0. A copy of the CTCAE version 4.0 can be downloaded from the CTEP web site
http://ctep.cancer.gov/protocolDevelopment/electronic_applications/ctc.htm.
- **For expedited reporting purposes only:**
 - AEs for the agent(s) that are listed above should be reported only if the adverse event varies in nature, intensity or frequency from the expected toxicity information which is provided.

The causal relationship to study drug is determined by the treating investigator and should be used to assess all adverse events (AE). The causal relationship can be one of the following:

- Related: There is a reasonable causal relationship between study drug administration and the AE.

- Not related: There is not a reasonable causal relationship between study drug administration and the AE.

The term "reasonable causal relationship" means there is evidence to suggest a causal relationship.

Adverse events can be spontaneously reported or elicited during open-ended questioning, examination, or evaluation of a subject. (In order to prevent reporting bias, subjects should not be questioned regarding the specific occurrence of one or more AEs.)

7.2.1 NON-SERIOUS ADVERSE EVENTS

Non-serious adverse events are to be provided to BMS in aggregate via a final study report as specified in the research agreement or, if a regulatory requirement [e.g. IND US trial] as part of an annual reporting requirement.

A non-serious adverse event is an AE not classified as serious (see **Section 7.3** below).

7.2.2 Non-serious Adverse Event Collection and Reporting

The collection of non-serious AE information should begin at initiation of study drug. All non-serious adverse events (not only those deemed to be treatment-related) should be collected continuously during the treatment period and for a minimum of 30 days following the last dose of study treatment.

Non-serious AEs should be followed to resolution or stabilization, or reported as SAEs if they become serious. Follow-up is also required for non-serious AEs that cause interruption or discontinuation of study drug and for those present at the end of study treatment as appropriate.

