2.2.6 Clinical Safety

Blockade of CTLA-4 by ipilimumab leads to T-cell activation, with the potential for clinical inflammatory adverse events (AEs) primarily involving the skin (dermatitis/pruritus), GI tract (diarrhea/colitis), liver (hepatitis), endocrine glands (e.g., hypophysitis and adrenal or thyroid abnormalities), and other less frequent organs (e.g., uveitis/episcleritis). The majority of these inflammatory AEs initially manifested during treatment; however, a minority occurred weeks to months after discontinuation of ipilimumab. The majority of the inflammatory AEs are reversible with the guidance issued in **Section 6**. In rare cases, these inflammatory AEs may be fatal.

Patients should be assessed for signs and symptoms of enterocolitis, dermatitis, neuropathy, and endocrinopathy, and clinical chemistries (including liver function, adrenocorticotrophic hormone [ACTH] level, and thyroid function tests) should be evaluated.

During evaluation of a suspected inflammatory AE, all efforts should be made to rule out neoplastic, infectious, metabolic, toxin, or other etiologic causes. Serological, immunological, imaging, and biopsy with histology (e.g., biopsy-proven lymphocytic) data should be used to support the diagnosis of an immune-mediated toxicity or support an alternative cause of the AE. In general, for severe inflammatory AEs, ipilimumab should be permanently discontinued, and systematic high-dose corticosteroid therapy should be initiated. For moderate immune-mediated AEs, ipilimumab should be held or delayed, and moderate-dose corticosteroids should be considered.

Based on limited current clinical experience, corticosteroids do not appear to adversely affect the anti-tumor response. For example, disease control was maintained in subjects with objective responses who received corticosteroid administration for concomitant serious inflammatory AEs.

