2.4 Ipilimumab with Nivolumab

2.4.1 Clinical Pharmacokinetics

The pharmacokinetics of nivolumab and ipilimumab were assessed using a PPK approach when nivolumab and ipilimumab were administered in combination. The %CV CL, V_{ss} , and $t_{1/2}$ of nivolumab were 10.0 mL/h (50.3%), 7.92 L (30.1%), and 24.8 days (94.3%), respectively. When ipilimumab 3 mg/kg (registration dose) was administered in combination with nivolumab, the CL of nivolumab was increased by 24%, whereas there was no effect on the CL of ipilimumab. However, co-administration with ipilimumab 1 mg/kg did not appear to have an effect on nivolumab CL. This is unlikely to be clinically relevant given the observed efficacy with the nivolumab and ipilimumab combination regimen.

When administered in combination, the CL of nivolumab increased by 42% in the presence of anti-nivolumab antibodies. There was no effect of anti-ipilimumab antibodies on the CL of ipilimumab.

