5.6 Duration of Follow Up

Participants will be followed for a minimum of 90 days following their last dose of ipilimumab and 100 days following their last dose of nivolumab for serious adverse event (SAE) reporting. Participants removed from protocol therapy for unacceptable adverse event(s) will be followed at minimum until resolution or stabilization of the adverse event. Participants who are removed before documented disease progression should be followed for RECIST response criteria until disease progression or death. Following documentation of disease progression, participants will continue to be followed for a maximum of 3 years or until death for survival status only.

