7.4 Expedited Adverse Event Reporting

7.4.1 Investigators **must** report to the Overall PI any serious adverse event (SAE) that occurs after the initial dose of study treatment, during treatment, or within 90 days of the last dose of ipilimumab or 100 days of the last dose of nivolumab on the local institutional SAE form.

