7.7 Expedited Reporting to Bristol-Myers Squibb (BMS)

All SAEs that occur following the subject's written consent to participate in the study through 90 days of discontinuation of dosing of ipilimumab and 100 days of discontinuation of nivolumab must be reported to BMS Worldwide Safety. If applicable, SAEs must be collected that relate to any later protocol-specified procedure (e.g., a follow-up biopsy).

The BMS SAE form should be used to report SAEs. The BMS protocol ID number must be included on the form that is submitted by the Investigator.

Following the subject's written consent to participate in the study, all SAEs, whether related or not related to study drug, are collected, including those thought to be associated with protocol-specified procedures. The investigator should report any SAE occurring after these time periods that is believed to be related to study drug or protocol-specified procedure. For drugs with potential for delayed SAEs (e.g., delayed excretion of the parent or active metabolites), a longer follow-up period may be warranted to allow collection of these SAEs, laboratory tests, and other

assessments.

For studies with long-term follow-up periods in which safety data are being reported, include the timing of SAE collection.

The Principal Investigator will reconcile the clinical database SAE cases transmitted to BMS Global Pharmacovigilance ([contact]). Frequency of reconciliation should be every 3 months and prior to the database lock or final data summary. BMS GPV&E will email, upon request from the Investigator, the GPV&E reconciliation report. Requests for reconciliation should be sent to [contact]. The data elements listed on the GPV&E reconciliation report will be used for case identification purposes. If the Investigator determines a case was not transmitted to BMS GPV&E, the case should be sent immediately to BMS.

In accordance with local regulations, BMS will notify investigators of all reported SAEs that are suspected (related to the investigational product) and unexpected (i.e., not previously described in the IB). In the European Union (EU), an event meeting these criteria is termed a Suspected, Unexpected Serious Adverse Reaction (SUSAR). Investigator notification of these events will be in the form of an expedited safety report (ESR).

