
A. A \pm 3 day scheduling window exists for this visit to accommodate vacations, holidays, adverse weather, or other scheduling difficulties.
 
B. The start of a subsequent cycle may be delayed by 7 days (+7 day window) to accommodate vacations, holidays, adverse weather, or other scheduling difficulties. The start of a subsequent cycle may also be moved up by 3 days (-3 day window) for scheduling issues.
 
C. Off-treatment evaluation. Note: follow up visits or other contact is required in order to identify SAEs during the 90 days following the last dose of ipilimumab and 100 days following the last dose of nivolumab. Participants removed from therapy due to adverse events must be followed at minimum until resolution or stabilization of the adverse event. Please refer to Section 5.6 for more detail.
 
D. Long-term follow up evaluation via telephone or care provider contact is required for survival status only for 3 years following documentation of disease progression, or until death. Contact to be performed every 3 months following the last dose of study treatment (\pm 1 month window).
 
E. Vital signs to include heart rate, blood pressure, temperature, and respiratory rate.
 
F. Serum chemistry to include sodium, potassium, chloride, CO₂, blood urea nitrogen (BUN), creatinine, glucose, albumin, total protein, alkaline phosphatase, total bilirubin, SGOT [AST], and SGPT [ALT]. Other tests may be ordered as clinically indicated.
 
G. Serum pregnancy test only required for women of childbearing potential. Childbearing potential defined as any female who has experienced menarche and who has not undergone successful surgical sterilization (hysterectomy, bilateral tubal ligation, or bilateral oophorectomy) or is not postmenopausal (defined as amenorrhea >12 consecutive months; or women with a documented plasma follicle-stimulating hormone level $>35\mu\text{IU}/\text{mL}$).
 
H. Nivolumab and ipilimumab infusions to be administered as described in Section 5.
 
I. Fresh tumor tissue biopsy as described in Section 9. Biopsy required at baseline prior to the administration of any study agents, and again on Cycle 1 Day 29 (\pm 7 day scheduling window). An optional biopsy at the time of disease progression will also be offered to all participants. Note that a germline blood sample is required with the pre-treatment tumor biopsy as described in Section 9.
 
J. PBMC collection to occur at baseline (any time prior to the first study drug administration), on Cycle 2 Day 1, and at the off treatment visit as described in Section 9.
									

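### New non-serious adverse events need be collected only to day 30 after the last dose, so late non-serious immune events can go unrecorded although contact to day 90/100 is already required

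*Combined protocol and SAP*

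**What the plan says.** - **Non-serious events.** Section 7.2.2 collects all of them, related or not, through treatment and "for a minimum of 30 days following the last dose of study treatment". Those already recorded are followed until they resolve or stabilize.
- **Serious events.** Section 5.6 sets a minimum follow-up of 90 days after the last ipilimumab dose and "100 days following their last dose of nivolumab for serious adverse event (SAE) reporting". Section 7.4 has the same limits ("within 90 days of the last dose of ipilimumab or 100 days of the last dose of nivolumab"), as does Section 7.7 ("through 90 days of discontinuation of dosing of ipilimumab and 100 days of discontinuation of nivolumab"). Section 7.7 adds: "The investigator should report any SAE occurring after these time periods that is believed to be related to study drug".
- **Contact after treatment.** Table 16 note C (Section 10) says that "follow up visits or other contact is required in order to identify SAEs during the 90 days following the last dose of ipilimumab", and likewise for 100 days after nivolumab. Its stated purpose is to find SAEs.
- **Timing of immune events.** Section 2.2.6 says most inflammatory events began during treatment, but "a minority occurred weeks to months after discontinuation of ipilimumab".
- **Use of the data.** Section 13.1 lists toxicity among the secondary objectives (Section 1.3 does not). Section 13.1.3 sets the toxicity population as everyone who received study drug, and Section 13.3.1 starts evaluability at the first dose. Neither gives an end to the observation period.

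**The concern.** The protocol recognizes delayed inflammatory events, and it keeps in touch with participants long enough to hear of many of them. For non-serious events, though, the duty to record new ones can end at day 30. A late skin, bowel or endocrine complaint managed in clinic could be known to the site and still be absent from the database.

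What is at stake is the secondary toxicity summary. Because 30 days is a minimum, some participants may be observed longer than others. Because Section 13 names no end point, a reader of the results could not tell what period the rates cover.

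**Working it through.** The plan gives no figure to reproduce here; the check compares its stated windows.

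**Inputs**

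| Item | Value | Source |
|---|---|---|
| New non-serious events | at least 30 days after last dose of study treatment | 7.2.2 |
| SAEs after ipilimumab | 90 days | 5.6, 7.4, 7.7, Table 16 note C |
| SAEs after nivolumab | 100 days | same |
| Dosing in a 42-day cycle | ipilimumab Day 1; nivolumab Days 1, 15, 29 | 5.1 |
| Maximum enrollment | 80 (43 if stopped after stage 1) | 13.1.2 |

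**Step 1: length of the gap.** Gap = SAE window minus non-serious minimum.
- Ipilimumab: 90 − 30 = 60 days; 60/90 = 67% of the SAE window.
- Nivolumab: 100 − 30 = 70 days; 70/100 = 70% of the SAE window.

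The 30 days run from the last dose of either drug. If that is a Day 29 nivolumab dose, the preceding ipilimumab dose was 28 days earlier. Collection then reaches 28 + 30 = 58 days after ipilimumab, and the ipilimumab gap shrinks to 90 − 58 = 32 days. The nivolumab gap stays at 70 days.

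**Step 2: which events fall in the gap.**

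| Event | Required to be recorded? |
|---|---|
| Serious, within 90/100 days | Yes (5.6, 7.4, 7.7) |
| Serious and believed related, later | Yes (7.7) |
| Potential drug-induced liver injury | Yes, handled as an SAE (7.2.4, 7.3) |
| Non-serious, starting by day 30 | Yes, and followed (7.2.2) |
| Non-serious, later becoming serious | Yes, as an SAE (7.2.2) |
| Non-serious, starting after day 30 and staying so | No |

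Only the last row is exposed.

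**Step 3: direction.** Against the rate over the full 90/100 days, an unrecorded event can only lower the estimate. The 80% confidence intervals in Section 13.1.3 reflect sampling error, not missed events.

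**Step 4: size.** The documents give neither a rate nor an onset distribution for late non-serious events, so the under-count cannot be computed. Two things can be said.
- Each participant whose only event of a given type is missed lowers that incidence by 1/80 = 1.25 percentage points, or 1/43 = 2.3 points if the trial stops after stage 1.
- As an illustration only, *assume* exponential onset after the last dose with half-time h. Then F(d) = 1 − 0.5^(d/h), and the share of new post-treatment events within 100 days that start after day 30 is 1 − F(30)/F(100).

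| Assumed h (days) | 7 | 14 | 24.8 | 45 | 60 |
|---|---|---|---|---|---|
| Share after day 30 | 5% | 22% | 40% | 53% | 57% |

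With uniform onset the share is 70/100 = 70%. These are shares of non-serious events that begin after the last dose, not of all toxicity. The spread shows how little can be concluded about magnitude.

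**The case against.** The scheme is tiered and internally consistent: a shorter minimum for non-serious events and a longer window for serious ones. A rate through 30 days after the last dose is a legitimate quantity, and in a single-arm trial no between-arm comparison is distorted. This stands. The point is an improvement, not an error or a contradiction.

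A reader might infer that delayed toxicity in general is missed. The second table in the working shows otherwise, since late serious events are covered. Section 7.8 also asks for all adverse events in routine submissions with no end date, but Section 7.2.2 remains the specific rule on how long new non-serious events are collected.

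A reader might also argue from drug persistence. With the 24.8-day combination half-life in Section 2.4.1, 2^(−30/24.8) = 43% of nivolumab remains at day 30 and 2^(−100/24.8) = 6% at day 100. That does not measure missed events. Residual concentration is not an onset rate, and the stated variability is 94.3%. Sections 2.3.6 and 2.3.7 report no pattern of events by nivolumab dose and a fairly flat exposure–safety relationship. The delayed-onset statement concerns ipilimumab.

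A longer window would not find everything. Table 16 schedules TSH only pre-study and on Day 1 of Cycle 2 onward, and chemistry ends at the off-treatment visit. Note C allows any form of contact and fixes no number or timing. Asymptomatic thyroid or enzyme changes would still be missed. This stands and limits the benefit.

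**Conclusion.** The point holds as a low-cost improvement to a secondary analysis. Following the plan as written, a non-serious immune event that first appears after day 30 and never becomes serious need not be recorded. The toxicity estimate can therefore be biased only downward relative to the rate over the 90/100-day windows.

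The gap in required collection is up to 60 days for ipilimumab and 70 days for nivolumab, but its effect on the rates cannot be sized from the documents. It would be too strong to say that the rates will be materially too low, or that participants who stop early are most affected. Sites may collect beyond the minimum, most inflammatory events begin on treatment, and nothing in the documents shows how missed events are distributed. Response rate, the two-stage rule, power and type I error are untouched.

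The conclusion assumes that Section 7.2.2 governs new non-serious events and that sites may stop at its minimum.

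**What to change.** 1. In Section 7.2.2, extend recording of new non-serious events to 90 days after the last ipilimumab dose and 100 days after the last nivolumab dose, for the immune categories in Section 6 (Tables 4 to 12). Leave the 30-day minimum for other non-serious events.
2. In Table 16 note C, say that the contacts already required also serve this purpose. Keep the questions open-ended, since Section 7.2 warns against asking about particular events. No new visits or laboratory tests are needed.
3. Record the start date of any later cancer therapy, and report late events separately before and after it.
4. In Section 13, state the toxicity observation window for serious and non-serious events. If step 1 is not adopted, say that non-serious events were required only to day 30.

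The cost is modest extra data entry. Some late events will be hard to separate from progression or next-line therapy; limiting the extension to the immune categories and dating later therapy reduces this but does not remove it. Laboratory changes without symptoms will still be missed, and the report should say so.
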